#### 6.1.1.5 Pulmonary Toxicity

Dyspnea, cough, fatigue, hypoxia, pneumonitis, and pulmonary infiltrates have been associated with the administration of atezolizumab and have primarily been observed in patients with underlying NSCLC.

Mild-to-moderate events of pneumonitis have been reported with atezolizumab. All pulmonary events should be thoroughly evaluated for other commonly reported etiologies such as pneumonia/infection, lymphangitic carcinomatosis, pulmonary embolism, heart failure, chronic obstructive pulmonary disease (COPD), or pulmonary hypertension. Recommended management for pulmonary events are listed in table 5 and may include the following exams:

- Measurement of oxygen saturation (i.e., arterial blood gas)
- High-resolution CT scan of the chest
- Bronchoscopy with bronchoalveolar lavage and biopsy
- Pulmonary function tests (with diffusion capacity of the lung for carbon monoxide [DLCO])

As a precaution, patients will be assessed for pulmonary signs and symptoms throughout the study.

**Table 5 Dose Modification Guidelines for Pulmonary Toxicity (Pneumonitis)**

Toxicity	Description	Management
Pulmonary toxicity (Pneumonitis)	Grade 1	
 
• Continue atezolizumab with close monitoring
 
• Re-evaluate on serial imaging
 
• Consider pulmonary consultation
 

	Grade 2	
 
• Hold and atezolizumab and start prednisone 60 mg/day or equivalent
 
• Consult pulmonary and infectious disease specialists with consideration for bronchoscopy/BAL
 
• When symptoms improve to Grade <math>\leq</math> 1, taper steroids over <math>\geq</math> 1 month to <math><</math> 10 mg/day
 
• First occurrence:               
 
○ Atezolizumab may be resumed if the event improves to Grade <math>\leq</math> 1 within 12 weeks and if corticosteroids have been reduced to the equivalent of oral prednisone <math>\leq</math> 10 mg/day
 
○ Permanently discontinue atezolizumab if event does not resolve to Grade 1 or better within 12 weeks from last dose of Atezolizumab and contact the PI. If the subject was unequivocally deriving clinical benefit, the subject may be able to resume as determined by the PI
 
 
 
• For recurrent events:               
 
○ Treat as Grade 3–4 (see below)
 
 
 

	Grade 3-4	
 
• Permanently discontinue atezolizumab, start prednisone 60 mg/day or equivalent and notify PI and study team.
 
• If symptoms are not improving after 48 hours or is worsening, add additional alternative immunosuppression (e.g., infliximab, cyclophosphamide, IVIG, or mycophenolate mofetil) to the corticosteroid regimen
 
• Consult pulmonary and infectious diseases as bronchoscopy/BAL is recommended
 
• When symptoms improve to Grade <math>\leq</math> 1, taper steroids over <math>\geq</math> 1 month
 
• If event resolves to Grade 1 or better within 12 weeks from last dose of atezolizumab, and if the subject was unequivocally deriving clinical benefit, the subject may be able to resume as determined by the PI
 

6.1.1.6 Potential Pancreatic Toxicity

Symptoms of abdominal pain associated with elevations of amylase and lipase, suggestive of pancreatitis, have been associated with administration of other immunomodulatory

agents. The differential diagnosis of acute abdominal pain should include pancreatitis. Appropriate workup should include an evaluation for obstruction, as well as serum amylase and lipase tests.

#### 6.1.1.7 Potential Eye Toxicity

An ophthalmologist should evaluate visual complaints. Uveitis or episcleritis may be treated with topical corticosteroid eye drops. Atezolizumab should be permanently discontinued for immune-mediated ocular disease that is unresponsive to local immunosuppressive therapy.

Ocular toxicity should be managed according to the guidelines in Table 6.

**Table 6 Dose Modification Guidelines for Eye Toxicity**

Toxicity	Description	Management
Eye toxicity (autoimmune uveitis, iritis, or episcleritis)	Symptomatic	
 
• Hold atezolizumab.
 
• Consult ophthalmologist and start topical corticosteroid eye drops.
 
• Atezolizumab may be restarted following resolution of the events.
 
• Permanently discontinue Atezolizumab for immune-mediated ocular disease that is unresponsive to local immunosuppressive therapy.
 

	Grade 1	
 
• Continue atezolizumab
 
• Referral to ophthalmologist strongly recommended
 
• Initiate treatment with topical corticosteroid eye drops/ topical immunosuppressive therapy
 
• If symptoms persist, treat as a Grade 2 event.
 

	Grade 2	
 
• Withhold atezolizumab for up to 12 weeks
 
• Referral to ophthalmologist strongly recommended
 
• Initiate treatment with topical corticosteroid eye drops/ topical immunosuppressive therapy
 
• Resume atezolizumab if event resolves to Grade 1 or better within 12 weeks from last dose of atezolizumab
 
• Permanently discontinue atezolizumab if event does not resolve to Grade 1 or better within from 12 weeks from last dose of atezolizumab.                             
 
○ If the subject was unequivocally deriving clinical benefit, the subject may be able to resume Atezolizumab as determined by the PI.
 
 
 

	Grade 3-4	
 
• Permanently discontinue Atezolizumab and contact PI                             
 
○ If the subject was unequivocally deriving clinical benefit, the subject may be able to
 
 
 

Toxicity	Description	Management
		resume Atezolizumab as determined by the PI.Refer to ophthalmologist 
 
• Initiate treatment with 1-2 mg/kg/day oral prednisone or equivalent
 
• If event resolves to grade 1 or better, taper corticosteroids over <math>\geq</math> 1 month.
 

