## **6. DOSING DELAYS/DOSE MODIFICATIONS**

Dose delays and modifications will be made as indicated in the following table(s). The descriptions and grading scales found in the revised NCI Common Terminology Criteria for Adverse Events (CTCAE) version 4.0 will be utilized for dose delays and dose modifications. A copy of the CTCAE version 4.0 can be downloaded from the CTEP website [http://ctep.cancer.gov/protocolDevelopment/electronic\\_applications/ctc.htm](http://ctep.cancer.gov/protocolDevelopment/electronic_applications/ctc.htm).

Dosing interruptions are permitted in the case of medical / surgical events or logistical reasons not related to study therapy (e.g., elective surgery, unrelated medical events, patient vacation, and/or holidays). Participants held for these reasons are required to resume therapy within 3 weeks of the scheduled interruption. The reason for interruption must be documented in the participant's medical record.

If there are dosing delays for any reason, all study assessments are to be delayed in the same fashion, such that that scans and other assessments occur in conjunction with cycles of treatment.

No dose reductions are allowed for atezolizumab.

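### Table 6 sets an ungraded Symptomatic row beside graded rows for the same eye toxicity, gives no precedence, and so tells a symptomatic Grade 1 patient both to hold and to continue atezolizumab

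*Combined protocol and SAP*

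**What the plan says.** Section 6.1.1.7 sends every eye event to one table: "Ocular toxicity should be managed according to the guidelines in Table 6". Section 6 states that the CTCAE version 4.0 descriptions and grading scales "will be utilized for dose delays and dose modifications".

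Table 6 then has four rows for one toxicity:

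- **Symptomatic** (no grade given): "Hold atezolizumab", consult an ophthalmologist, start topical steroid drops. On restart: "Atezolizumab may be restarted following resolution of the events". On stopping: "Permanently discontinue Atezolizumab for immune-mediated ocular disease that is unresponsive to local immunosuppressive therapy".
- **Grade 1**: continue, with topical treatment. Then: "If symptoms persist, treat as a Grade 2 event".
- **Grade 2**: withhold for at most 12 weeks, with topical treatment. Resume if the event falls to Grade 1 or lower by 12 weeks after the last dose, and otherwise stop permanently. The PI may allow a patient who is clearly benefiting to resume.
- **Grade 3-4**: "Permanently discontinue Atezolizumab and contact PI", with oral prednisone at 1-2 mg/kg/day. The same PI exception applies.

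The text of Section 6.1.1.7 repeats the stopping condition of the Symptomatic row: "Atezolizumab should be permanently discontinued for immune-mediated ocular disease that is unresponsive to local immunosuppressive therapy".

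**The concern.** A dose-modification table works only if each event falls in one row, or if a rule says which row wins. Table 6 classifies one toxicity on two axes, symptoms and grade, and has no such rule. A patient with a symptomatic graded event matches two rows.

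Section 7.1.3.1 lists ocular toxicities among the adverse events of special interest. If two rows apply, two investigators can take different decisions about drug and steroids for the same event. Each could point to a row that supports the decision, and a monitor could not say which of them deviated.

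**Working it through.** No sample size, power or error rate is involved. The check sets the rows side by side and then looks for a rule that chooses between them.

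**1. Do the rows overlap?** Yes, on three grounds within the protocol.

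- The Grade 1 row speaks of symptoms that persist ("If symptoms persist, treat as a Grade 2 event"), so the table itself expects symptomatic graded events.
- Section 6 applies CTCAE grades to dose modification, so a symptomatic eye event also carries a grade.
- The myocarditis table in Section 6.1.1.8 labels its single row Symptomatic and applies it to every grade. In this protocol the label does not mean ungraded.

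Tables 1, 2, 3 and 5 are keyed to grade alone. Table 4 uses symptoms for thyroid events and grade for hyperglycemia and hypophysitis. Only Table 6 uses both axes for one toxicity.

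**2. What does each row require of a symptomatic patient?**

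| Event | Symptomatic row | Graded row | Result |
|---|---|---|---|
| Grade 1 | Hold | Continue | Direct contradiction |
| Grade 2, first step | Hold, topical drops | Withhold, topical treatment | Agree |
| Grade 2, restart | After resolution (undefined); no time limit in the row | Grade 1 or lower by 12 weeks after last dose | Differ |
| Grade 2, permanent stop | No response to local treatment | Grade 1 not reached by 12 weeks, subject to PI exception | Differ |
| Grade 3-4 | Hold, topical drops, may restart after resolution | Permanent stop and oral prednisone, subject to PI exception | Differ in drug status and steroid route |

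**3. How wide is the Grade 2 difference?** The Symptomatic row gives no time limit, but Section 6.1.1 caps a toxicity hold at 84 days beyond the scheduled infusion. With a 21-day cycle, and ignoring visit windows:

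- Grade 2 row: 12 × 7 = 84 days from the last dose.
- General cap: 21 + 84 = 105 days from the last dose.
- Gap: 105 − 84 = 21 days.

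Take an event that responds to drops, is still above Grade 1 at day 84, and resolves at week 14 (14 × 7 = 98 days). The Symptomatic row lets it restart, within the cap. The Grade 2 row stops the drug permanently unless the PI exception is used.

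The restart threshold may differ too. An event at Grade 1 by week 8 resumes under the Grade 2 row. Under the Symptomatic row the answer depends on what resolution means, and the row does not say.

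**4. Does other text choose a row?** No.

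- Section 6 says that grades are used, but not that a graded row overrides the Symptomatic row.
- Section 6.1 generally continues drug for Grade 1 to 2 events. That fits the Grade 1 row but not the Grade 2 row, which withholds.
- For higher grades Section 6.1 withholds drug and gives oral or parenteral steroids. That matches neither Table 6 row fully. It requires a permanent stop for life-threatening events, which narrows the conflict for those events only.
- Section 6.1.1.7 points back to Table 6.

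**The case against.** The best counter-argument is that a sensible investigator would read the table by grade. Section 6 supports that reading, and Section 6.1 gives direction for Grade 1 and for life-threatening events. This has some force, but it is inference. No text subordinates the Symptomatic row, and Section 6.1 itself disagrees with the Grade 2 row.

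Other objections limit the point, and they stand:

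- A reader might infer that the Symptomatic row orders a different action at every grade. It does not. For Grade 2 both rows hold and both use topical treatment.
- A reader might take the Symptomatic row to require complete resolution. The word complete is not there. Section 6.1.1.1 speaks of the resolution of colitis, while Table 1 resumes Grade 2 colitis at Grade 1 or lower. On that looser usage the two Grade 2 restart thresholds could coincide, which would leave the time limit and the stop trigger as the differences.
- A reader might infer that failure of local treatment is the only ground for a permanent stop. Section 6.1.1.7 and the Symptomatic row state it as a ground, not as the only one, so a further ground at Grade 3-4 does not by itself contradict them.
- For Grade 3-4, restart under the Symptomatic row is permissive, and the graded row has its own PI exception. The conflict is therefore not absolute. The exception is discretionary, however. It does not say which row applies, and it does not reach Grade 1.

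**Conclusion.** The point holds as an internal inconsistency in a safety instruction. There is a direct contradiction for symptomatic Grade 1 events (hold against continue). For symptomatic Grade 3-4 events the instructions differ, softened only by the PI exception. For symptomatic Grade 2 events the difference is confined to the restart and permanent-stop rules, including a 21-day window after day 84 under the assumptions above.

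It would be tempting to add that time on treatment or discontinuation for toxicity becomes uninterpretable. The documents do not support that. Section 13 defines neither as an endpoint, Section 13.7 summarizes toxicity by maximum grade, and Section 13.8.1 keeps everyone who starts protocol therapy in the efficacy population even with major deviations. The protocol gives no ocular event rate for this regimen, so the number of patients affected cannot be estimated. Sample size, power and the primary PFS analysis are not affected.

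The conclusion rests on one assumption, which the Grade 1 row supports: that an eye event can be symptomatic and graded at once. It should be corrected, but it does not threaten the trial's main conclusion.

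**What to change.** The sponsor should make each eye event in Table 6 map to one instruction. The Symptomatic row could be removed or merged into the graded rows. Alternatively, it could stay with a sentence saying which row governs when two apply. If it stays, the table should define resolution and say whether a time limit and the PI exception apply to that row. Section 6.1.1.7 and the general guidance in Section 6.1 should then be aligned with the result.

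Which hold, restart, steroid and stopping rules stand is a clinical decision for the sponsor; this point does not choose among them. The cost is one table edit and matching text in the next amendment, with no extra visits, data or patients.

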#### 6.1.1.8 Potential Cardiac Toxicity

Myocarditis refers to a diverse group of heart-specific immune processes classified by a spectrum of clinical and histopathological manifestations. It may present as mild dyspnea or chest pain, or more severe cardiogenic short or sudden death. In the absence of an infectious etiology, immune-related myocarditis is confirmed by histological evidence of inflammatory infiltrates within the myocardium, together with cardiac myocytes degenerations and necrosis of non-ischemic origin.

A cumulative analysis of the company safety database which includes data from clinical trials and post-marketing setting (data cut-off 20 February 2017), identified 2 non-fatal cases of myocarditis, including one with biopsy confirmation. Approximately 8, 000 clinical trial patients and 5, 000 post-marketing patients have been treated with Atezolizumab to date.

Atezolizumab should be permanently discontinued for all grades of myocarditis. Corticosteroids and/or additional immunosuppressive agents should be administered as clinically indicated.

Toxicity	Description	Management
Myocarditis	Symptomatic	
 
• Permanently discontinue Atezolizumab for any grade and notify PI and study team.
 
• Corticosteroids and/or immunosuppressive agents should be administered as clinically indicated.
 
• Consult a cardiologist.
 

## 7. ADVERSE EVENTS: LIST AND REPORTING REQUIREMENTS

Adverse event (AE) monitoring and reporting is a routine part of every clinical trial. The following list of reported and/or potential AEs (Section 7.1) and the characteristics of an observed AE (Section 7.2) will determine whether the event requires expedited reporting **in addition** to routine reporting.

### 7.1 Adverse Events Lists

#### 7.1.1 Expected adverse events for atezolizumab

The PD-L1/PD-1 pathway is involved in peripheral tolerance; therefore, such therapy may increase the risk of immune-related AEs, specifically the induction or enhancement of

autoimmune conditions. AEs with potential immune-related causes, including rash, hypothyroidism, hepatitis/transaminitis, colitis, myositis, and myasthenia gravis, have been observed with Atezolizumab in Study PCD4989g.

Although most immune-related AEs observed with immunomodulatory agents have been mild and self-limiting, such events should be recognized early and treated promptly to avoid potential major complications[Charniat *et al.*, 2016].

A more detailed safety profile of Atezolizumab is provided in the Atezolizumab Investigator's Brochure.

### 7.1.2 Safety Parameters and Definitions

#### Specification of Safety Variables

Safety assessments will consist of monitoring and reporting adverse events (AEs) and serious adverse events (SAEs) per protocol. This includes all events of death, and any study specific issue of concern.

#### Adverse Events

An AE is any unfavorable and unintended sign, symptom, or disease temporally associated with the use of an investigational medicinal product (IMP) or other protocol-imposed intervention, regardless of attribution.

This includes the following:

- AEs not previously observed in the patient that emerge during the protocol-specified AE reporting period, including signs or symptoms that were not present prior to the AE reporting period
- Complications that occur as a result of protocol-mandated interventions (e.g., invasive procedures such as cardiac catheterizations).
- If applicable, AEs that occur prior to assignment of study treatment associated with medication washout, no treatment run-in, or other protocol-mandated intervention.
- Preexisting medical conditions (other than the condition being studied) judged by the investigator to have worsened in severity or frequency or changed in character during the protocol-specified AE reporting period.
- 

#### Serious Adverse Events

An AE should be classified as an SAE if the following criteria are met:

- It results in death (i.e., the AE causes or leads to death).
- It is life threatening (i.e., the AE, in the view of the investigator, places the subject at immediate risk of death. It does not include an AE that, had it occurred in a more severe form, might have caused death.).
- It requires or prolongs inpatient hospitalization.
- It results in persistent or significant disability/incapacity (i.e., the AE results in substantial disruption of the subject's ability to conduct normal life functions).
- It results in a congenital anomaly/birth defect in a neonate/infant born to a mother exposed to the IMP.

- It is considered a significant medical event by the investigator based on medical judgment (e.g., may jeopardize the subject or may require medical/surgical intervention to prevent one of the outcomes listed above).

### 7.1.3 Adverse Event Characteristics

**CTCAE term (AE description) and grade:** The descriptions and grading scales found in the revised NCI Common Terminology Criteria for Adverse Events (CTCAE) version 4.0 will be utilized for AE reporting. All appropriate treatment areas should have access to a copy of the CTCAE version 4.0. A copy of the CTCAE version 4.0 can be downloaded from the CTEP web site [http://ctep.cancer.gov/protocolDevelopment/electronic\\_applications/ctc.htm](http://ctep.cancer.gov/protocolDevelopment/electronic_applications/ctc.htm).

**For expedited reporting purposes only:**

AEs for the agent(s) that are listed above should be reported only if the adverse event varies in nature, intensity or frequency from the expected toxicity information which is provided.

**Attribution of the AE:**

Definite – The AE *is clearly related* to the study treatment.

Probable – The AE *is likely related* to the study treatment.

Possible – The AE *may be related* to the study treatment.

Unlikely – The AE *is doubtfully related* to the study treatment.

Unrelated – The AE *is clearly NOT related* to the study treatment.

#### 7.1.3.1 Adverse Events of Special Interest

The following AEs are considered of special interest and must be reported to the [REDACTED] Drug Safety expeditiously, irrespective of regulatory seriousness criteria:

- Cases of potential drug-induced liver injury that include an elevated ALT or AST in combination with either an elevated bilirubin or clinical jaundice, as defined by Hy's Law and based on the following observations:
  - Treatment-emergent ALT or AST > 3 x baseline value in combination with total bilirubin > 2 x ULN (of which  $\geq$  35% is direct bilirubin)
  - Treatment-emergent ALT or AST > 3 x baseline value in combination with clinical jaundice Suspected transmission of an infectious agent by the study treatment, as defined below:
    - Any organism, virus, or infectious particle (e.g., prion protein transmitting transmissible spongiform encephalopathy), pathogenic or non-pathogenic, is considered an infectious agent. A transmission of an infectious agent may be suspected from clinical symptoms or laboratory findings that indicate an infection in a patient exposed to a medicinal product. This term applies only when a contamination of study treatment is suspected.
- Pneumonitis
- Colitis

- Endocrinopathies: diabetes mellitus, pancreatitis, adrenal insufficiency, hyperthyroidism, and hypophysitis
- Hepatitis, including AST or ALT > 10xULN
- Systemic lupus erythematosus
- Neurological disorders: Guillain-Barré syndrome, myasthenic syndrome or myasthenia gravis, and meningoencephalitis
- Events suggestive of hypersensitivity, infusion-related reactions, cytokine release syndrome, influenza-like illness, systemic inflammatory response syndrome, and systemic immune activation
- Nephritis
- Ocular toxicities (e.g., uveitis, retinitis) Myositis Myopathies, including rhabdomyolysis
- Grade  $\geq$  2 cardiac disorders (e.g., atrial fibrillation, myocarditis, pericarditis)

## **7.2 Methods and Timing for Assessing AND Recording Safety variables**

The investigator is responsible for ensuring that all AEs and SAEs that are observed or reported during the study, are collected and reported to the FDA, appropriate IRB(s), and [REDACTED] in accordance with CFR 312.32 (IND Safety Reports).

### **7.2.1 Adverse Event Reporting Period**

The study period during which all AEs and SAEs must be reported begins after informed consent is obtained- and initiation of study treatment and ends 30 days following the last administration of study treatment or study discontinuation/termination, whichever is earlier. After this period, investigators should only report SAEs that are attributed to prior study treatment.

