## 7.4 Reporting to Principal investigator

- 7.4.1 Investigators **must** report to the Overall PI any serious adverse event (SAE) that occurs after the initial dose of study treatment, during treatment, or within 30 days of the last dose of study treatment on the local institutional SAE form within 1 business day of awareness. Report serious adverse events by telephone, email, or facsimile to:

[name]

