## 9.4 Cerebrospinal fluid (CSF)

### 9.4.1 Collection

While CSF collection is optional, it will be encouraged. We plan to collect CSF for at least 10 patients at baseline for cytology and potential DNA isolation, before cycle 3 day 1, and at progression or off protocol therapy, whichever comes first. The samples will be banked in the DFCI breast tissue repository for these and future research purposes. These specimens will become the property of the DF/HCC.

The following CSF blood samples are optional\*:

Screening (baseline):

- 3-10 mL in sterile collection tubes

Cycle 2 Day 15 to day 21:

- 3-10 mL in sterile collection tubes

Off Treatment (at progression or off protocol therapy, whichever comes first):

- 3-10 mL in sterile collection tubes

\*Streck Cell-Free DNA BCT tubes may be used in place of sterile collection tubes. After collection, gently invert tube 10 times to ensure proper mixing of stabilization agent and store at room temperature until processing.

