- h. CT and/or MRI should be of the chest, abdomen and pelvis. Additional imaging studies (CT neck, plain films, etc.) are permitted as clinically indicated. The same radiographic procedures and technique must be used throughout the study for each patient. Assessments should be done during the last 15-21 days of a cycle, q6weeks for the first 24 weeks (i.e. C2, 4, 6, 8) and then can be reduced to q9 weeks (i.e. C11, 14, 17, etc.) until progression. For those taken off-study for reasons other than progressive disease, tumor measurements should continue to be repeated every 6-12 weeks until progression or beginning a new cancer therapy regimen. Failure to complete restaging after a patient has been taken off protocol therapy will not constitute a protocol violation.
- i. Hematology: hemoglobin, hematocrit, platelet count, RBC count, WBC count, percent and absolute differential count.
- j. Chemistry: sodium, potassium, chloride, bicarbonate, glucose, BUN, creatinine, calcium, total bilirubin, total protein, albumin, ALT, AST, alkaline phosphatase, and LDH.
- k. Beginning with cycle 4, TSH will be done every other cycle on Day 1 (i.e. cycles 4, 6, 8, etc.).
- l. In female subjects of child-bearing potential as defined in the eligibility criteria, serum or urine pregnancy test must be performed within **8 days** prior to initiating protocol therapy
- m. cfDNA is required to be drawn on C1D1, Day 1 of RT, C3D1, C5D1, C9D1, at each restaging visit, and at disease progression or discontinuation of protocol therapy, whichever comes first.
- n. Immune markers will be drawn on C1D1, Day 1 of RT, C3D1, C5D1, C9D1, and at disease progression or discontinuation of protocol treatment, whichever comes first.
- o. Baseline tumor biopsy should be obtained within 28 days of the first dose of Atezolizumab. The C2D1 biopsy should be performed as close to C2D1 as possible but may be collected between C2D1 and C2D21. Both the baseline and C2 biopsy are required for participants with accessible disease outside of the field of radiotherapy. A biopsy at the time of disease progression is optional for subjects who have accessible disease and have achieved an objective response (CR or PR) and/or experienced prolonged stable disease for ≥ 24 weeks.
- p. CSF collection will be performed at baseline, C2 day 15 to day 21, and at disease progression or discontinuation of protocol therapy, whichever comes first (±3 days) in at least 10 participants.

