### Risks of Research Biopsy and Procedures for Minimizing Risk

#### Potential risks according to site are:

*Skin/chest wall (punch biopsy):*

- Likely: local discomfort and minor bleeding
- Less likely: moderate or major bleeding, or infection

*Lymph node, liver, or bone (core needle biopsy):*

- Likely: local discomfort and minor bleeding
- Less likely: moderate or major bleeding, need for blood transfusion, hospitalization due

to bleeding or other complications, infection, damage to adjacent organs. Additional risks may be

present if intravenous conscious sedation is required

*Breast (core biopsy):*

- Likely: local discomfort and minor bleeding.
- Less likely: moderate or major bleeding, need for blood transfusion, hospitalization due

to bleeding or other complications, infection, pneumothorax, damage to adjacent organs.

*Pleural fluid (thoracentesis):*

- Likely: local discomfort and minor bleeding
- Less likely: moderate or major bleeding, need for blood transfusion, hospitalization due to bleeding or other complications, infection, pneumothorax, damage to adjacent organs

*Ascites fluid (paracentesis):*

- Likely: local discomfort and minor bleeding
- Less likely: moderate or major bleeding, need for blood transfusion, hospitalization due to bleeding or other complications, infection, bowel perforation or damage to adjacent organs. In order to minimize the risk of a biopsy, only qualified personnel will perform these procedures.

Prior to the procedure, the physician performing the procedure will discuss the risks with each study participant, answer any questions, and obtain separate procedure consent. Patients will be evaluated for comorbidities or concomitant medications that may increase the risk of potential complications. For biopsies of lesions that are not superficial and clearly palpable, imaging studies such as CT or ultrasound will be used to guide the biopsy in order to minimize the risk of damage to adjacent structures. After lymph node biopsies, patients will be observed after the procedure, or according to standard institutional guidelines. After liver biopsies, patients will be observed a minimum of 4 hours (range 4-6 hours) after the procedure, or according to standard institutional guidelines. Less than the goal quantity of tissue is accepted for each type of biopsy, and will be left to the clinical judgment of the physician performing the procedure.

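### Sections 7.2.1 and 7.4.1 start AE and SAE reporting at first dose, so a pre-dose complication of the required baseline biopsy is an adverse event by definition but falls outside the stated period

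*Combined protocol and SAP*

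**What the plan says.** Section 7.2.1 states: "The study period during which all AEs and SAEs must be reported begins after informed consent is obtained- and initiation of study treatment". The period ends 30 days after the last study treatment, or at study discontinuation if that is earlier. After it closes, only SAEs attributed to prior study treatment need be reported. Section 7.4.1 asks investigators to send the Overall PI "any serious adverse event (SAE) that occurs after the initial dose of study treatment", up to 30 days after the last dose. Section 7.3.2.2 requires deaths to be reported when they occur within the 7.2.1 period.

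The definition of an adverse event in Section 7.1.2 is wider. It includes "Complications that occur as a result of protocol-mandated interventions (e.g., invasive procedures such as cardiac catheterizations" and, with the qualifier that this be applicable, "AEs that occur prior to assignment of study treatment associated with medication washout, no treatment run-in, or other protocol-mandated intervention".

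The study calendar (Section 10) marks an adverse event evaluation in the screening column, day -28 to day -1. Its footnote o says: "Baseline tumor biopsy should be obtained within 28 days of the first dose of Atezolizumab". The same footnote and Section 9.2.1 require this biopsy when disease is accessible. Baseline CSF is optional; Section 9.4.1 says "We plan to collect CSF for at least 10 patients at baseline for cytology and potential DNA isolation". For lymph node, liver and bone cores, Appendix H lists among the less likely risks "moderate or major bleeding, need for blood transfusion", hospitalization, infection and damage to adjacent organs. It also describes the risks of sedation.

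**The concern.** The baseline biopsy is taken for research. When the protocol requires a procedure, its complications belong in the trial's safety reporting whether or not the drug has been given. Here the definition and the calendar tell staff to look for such events, while the section that sets the reporting period does not require them to be reported.

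A description of the trial's procedural risk built on the stated window would include complications of the cycle 2 biopsy and omit those of the baseline biopsy, although the procedure and its listed risks are the same. A participant whose complication prevents her from starting treatment would never enter the window.

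**Working it through.** There is no stated figure to reproduce. The check sets the sections side by side and follows one case through them.

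**When the window opens.** Section 7.2.1 joins consent and treatment initiation with 'and', so the later of the two governs. Section 7.4.1 reaches the same start in separate wording.

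**Where the procedures fall.**

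| Procedure | Timing | Status | Inside the 7.2.1 period? |
|---|---|---|---|
| Baseline biopsy | Before dose 1 | Required if accessible; may be waived for the first 6 participants | No, until dose 1 |
| Cycle 2 biopsy | C2D1 to C2D21 | Required if accessible; same waiver | Yes |
| Baseline CSF | Screening | Optional, at least 10 planned | No, until dose 1 |
| Cycle 2 CSF | C2 day 15 to 21 | Optional | Yes |
| CSF at progression or off therapy | After dose 1 | Optional | Only within 30 days of last treatment |

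**One case.** Take a participant admitted with a bleed after a liver biopsy on day -5.
- Section 7.1.2: a complication of a protocol-mandated intervention, hence an adverse event. Inpatient hospitalization makes it serious.
- Section 7.2.1: before treatment initiation, hence outside the period.
- Section 7.4.1: before the initial dose, hence outside the duty to report SAEs to the Overall PI.
- Section 7.3.2.2: if fatal before dose 1, outside the period for death reporting.
- Section 13.8.2: if she never starts, she is not in the safety population, which requires at least one dose.

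**Do other sections close the gap?** Section 7.2 makes the investigator responsible for all events during the study. Section 7.5 asks for all SAEs, Section 7.6 refers to IRB policy, and Section 7.9 sends Grade 2 or higher events to the Overall PI. None gives a start date. Section 7.2.1 is the only section that defines the period, so a site must choose between a specific rule and several general ones.

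**Bounds on the exposure.**
- Number of baseline biopsies: at most 45, the target enrollment. If all six run-in participants are waived, at most 45 - 6 = 39. Inaccessible disease lowers this further, and Appendix H does not mandate lung cores.
- Interval before dose 1: at most 28 days by footnote o. Table 9-1 instead places the baseline biopsy 2 to 7 days before radiation, and Section 5.1 places dose 1 in the same range. On those texts the interval is at most 7 - 2 = 5 days.
- Complication rate: the documents give none, so no expected number of missed events can be calculated.

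**The case against.** The strongest reply is that the wording mismatch is real but its consequences are small and uncertain. Much of that stands. A reader might infer four stronger things, and the documents support none of them.

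- *The PI, the DSMC and the IRB would not see these events.* Sections 7.2, 7.5, 7.6 and 7.9 set duties with no first-dose start, and the IRB policy is not in the documents. For registered participants, Section 4.1 also sends issues that would delay treatment to the Overall PI.
- *No safety record would remain for a participant who never starts.* Section 4.1 cancels the registration only. It says nothing about removing source records or the screening AE evaluation.
- *The events could not trigger action.* No formal rule acts on biopsy complications before or after dose 1. Section 5.4 limits DLTs to events related to drug or radiation, and the boundaries in Section 13.4 concern DLTs and radiation toxicity. DSMC review under Section 12.2 is broader and discretionary.
- *Appendix H documents the risks of CSF collection.* It does not cover that procedure. Because CSF collection is optional, the bullets on mandated interventions fit the biopsy better; CSF fits only the broader wording in Section 7.1.2 on protocol-imposed interventions.

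The other side can also say that the stray hyphen in Section 7.2.1 points to a garbled edit, that the pre-treatment bullet in Section 7.1.2 is conditional, and that its examples look generic. These are fair points. But Section 7.4.1 repeats the first-dose start in clean wording, and the bullet on procedure complications carries no such condition. If a consent start was intended, both sections still need correcting.

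**Conclusion.** The concern holds as an internal contradiction with a safety consequence. On the stated window, a serious or fatal complication of the required baseline biopsy before dose 1 falls outside the AE/SAE period and outside SAE reporting to the Overall PI. The same complication of the cycle 2 biopsy falls inside both. The general duties elsewhere make the text ambiguous without resolving it.

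The size is bounded by 45 baseline biopsies and 28 days per participant, and is probably smaller on both counts. The conclusion assumes that Section 7.2.1, as the specific rule, governs the general ones. If a site reads it the other way, these events would be reported and practice would differ between readers of the same protocol. No efficacy analysis, DLT count or stopping boundary is affected. It should be corrected because the procedure is required for research and the correction is cheap.

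**What to change.** In Sections 7.2.1 and 7.4.1:
- Start the period at informed consent for AEs and SAEs related to protocol research procedures: the baseline biopsy and its sedation, and baseline CSF collection when the participant opts in.
- State that this includes consented participants who never receive study treatment.
- Keep first dose as the start for all other AEs, and keep the existing one-business-day timeline for SAEs.

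The death rule in Section 7.3.2.2 then follows through its cross-reference. Present the procedure-related events in a separate listing, so that on-treatment toxicity in Section 13.7 is unchanged and participants outside the safety population are still shown. The form needs a place to record relatedness to the procedure, because Section 7.2.2 asks only about atezolizumab. The biopsy timing in Table 9-1 and calendar footnote o should be reconciled in the same amendment.

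The cost is amended wording, one listing and a few more SAE forms, with no new visits or procedures.
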